#### Neuropsychological Assessment

In addition to the clinical rating scales, the proposed investigation also includes a brief battery of neuropsychological tests to examine the potential effects of CBD on cognition in subjects with anxiety. Individuals will complete neuropsychological assessments at two time points; at baseline and after 6 weeks of treatment. The neurocognitive battery is primarily designed to evaluate frontal, executive, and memory functions as well as general intellectual capacity. The neuropsychological measures will be administered by a trained psychometrician and were chosen because they are standard, well-known measures that can be administered and scored reliably. Measures to be administered at baseline and both follow-up visits include the [REDACTED]

[REDACTED]. The neurocognitive assessment battery will take approximately 1.5 hours to complete. Many of these tests, including the [REDACTED] [REDACTED] have alternate versions to use at the follow-up visit, in order to reduce the likelihood that subjects remember portions of the assessments from baseline.

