## **SPECIFIC AIMS**

Concisely state the objectives of the study and the hypothesis being tested.

The proposed investigation is designed to examine the impact of 6 weeks of treatment with a sublingual high-cannabidiol industrial hemp-derived compound on individuals with symptoms of anxiety.

**Specific Aim 1:** To assess pre- and post-hemp treatment clinical state ratings of anxiety and quality-of-life ratings in individuals with symptoms of anxiety.

**Specific Aim 2:** To assess pre- and post-hemp treatment performance on a range of neurocognitive measures designed to examine cognitive function.

**Specific Aim 3:** In a subset of individuals, to examine structural and functional changes that may occur in the brain following treatment with a high-CBD hemp product using multimodal magnetic resonance imaging (MRI) techniques.

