A total of 52 (12 in the open-label phase, and 40 in the double-blind phase) female and male participants with anxiety, of minimum age 18, will complete a baseline visit including clinical ratings, an assessment of conventional medication use, quality of life measures, a neuropsychological test battery, a buccal swab sample, and optional neuroimaging (in a subset of participants who are eligible). Participants will subsequently be treated for 6 weeks with the CW sublingual solution. All participants will self-administer 0.5 ml (15 mg of CBD) of solution twice daily (BID). Participants will return to the laboratory or complete remote visits each week to complete clinical ratings and check in with study staff. After 6 weeks of treatment, participants will complete final clinical scales and quality of life measures, a complementary neuropsychological battery, and a corresponding neuroimaging component (where applicable). The open-label phase of the study is expected to take approximately 12 months to complete, and will assess the efficacy of the dose chosen for the double-blind study.

40 female and male participants will be enrolled in the double-blind phase. Study procedures will remain the same as the open-label phase, however participants will receive CW solution or placebo solution in a double-blind, randomized fashion. All participants will self-administer 0.5ml of solution BID for 6 weeks. The double-blind phase of the study is expected to take 24 months to complete.

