#### **STATISTICAL APPROACHES**

All statistical analyses will be conducted using IBM SPSS Statistics (version 28). Data will be screened for outliers and any data points more than 2 standard deviations from the group means will be excluded. Additionally, data will be screened for skew, kurtosis, non-normality, and homogeneity of variance. If the assumptions of parametric inferential analyses are not met, the appropriate non-parametric analyses (e.g. Wilcoxon-Signed Rank Test) will be performed. Descriptive statistics will be used to characterize the demographic data. Baseline clinical and neuropsychological data will be assessed using 2-tailed paired *t*-tests to compare follow-up timepoints to baseline values. When needed, Bonferroni corrections for multiple comparisons will be utilized.

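### Alternate test forms appear to be reserved for the follow-up visit, so with only paired tests planned, a difference in form difficulty would read as a cognitive effect of the product

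*Combined protocol and SAP*

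**What the plan says.** Aim 2 (Specific Aims) is a before-and-after question: "To assess pre- and post-hemp treatment performance on a range of neurocognitive measures designed to examine cognitive function". It names no comparison with placebo.

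The Neuropsychological Assessment section sets the schedule: "Individuals will complete neuropsychological assessments at two time points; at baseline and after 6 weeks of treatment". It then describes the alternate forms. The sentence opens "Many of these tests, including the", followed by redacted test names, and goes on to say that these tests "have alternate versions to use at the follow-up visit, in order to reduce the likelihood that subjects remember portions" of the first session. So the forms exist for many tests, not all. Research Design and Methods is in keeping with this, since it calls the final battery complementary to the baseline one. Nothing is said about counterbalancing, randomised form order or equating of the forms.

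Statistical Approaches gives the analysis: "Baseline clinical and neuropsychological data will be assessed using 2-tailed paired" t-tests of follow-up against baseline. The non-parametric example, the Wilcoxon signed-rank test, is also a paired test. No between-arm test or treatment-by-time term is stated for cognition.

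The open-label phase enrols 12 subjects, all on active product. The double-blind phase enrols 20 per arm under the same procedures.

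The Neuropsychological Assessment section also contains the phrase "Measures to be administered at baseline and both follow-up visits include the", which does not fit the two time points it has just set.

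**The concern.** Alternate forms are a sensible guard against subjects remembering items. The difficulty is the order. If everyone meets one form at baseline and the other at week 6, a change in score mixes two things: what happened to the subject, and how the two forms differ in difficulty. A slightly easier second form looks like cognitive improvement on the product. A slightly harder one looks like impairment, or hides a real gain.

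The planned paired test cannot separate the two, and neither can any later analysis of one arm alone. At stake is the interpretation of Aim 2 in the open-label phase and of any within-arm cognitive change reported from the double-blind phase.

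**Working it through.** **Plan's own figure.** There is none. The document gives no SD, effect size, power or alpha for Aim 2.

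**Inputs from the document.** Open-label n = 12; double-blind 20 per arm; two test occasions; two-tailed paired t-test.

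**Assumptions not in the document.** Alpha 0.05; no true change and no practice effect; form difference d of 0.1 to 0.5 SD; test-retest correlation r of 0.6 to 0.8. The 2-SD outlier exclusion in Statistical Approaches and dropout are not modelled.

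**Formula.** In units of the score SD, the change has SD √(2(1 − r)). Under fixed form order its mean is d. The paired t statistic is then noncentral t with n − 1 degrees of freedom and noncentrality d√n / √(2(1 − r)).

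**Example, d = 0.2, r = 0.7.** The SD of change is √0.6 = 0.775, so the standardised shift is 0.2 / 0.775 = 0.258.
- n = 12: noncentrality 0.258 × √12 = 0.894, critical value 2.201, rejection rate 13.0%.
- n = 20: noncentrality 0.258 × √20 = 1.155, critical value 2.093, rejection rate 19.5%.

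A simulation with 20,000 runs gave 12.6% and 19.6%, with a mean change of 0.20 SD in both. The form difference enters in full.

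**Rejection rate with no true change, r = 0.6 to 0.8 (nominal 5%):**

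| Form difference | n = 12 | n = 20 |
|---|---|---|
| 0.1 SD | 6.5-8% | 8-10% |
| 0.2 SD | 11-17% | 16-27% |
| 0.3 SD | 19-32% | 30-52% |
| 0.5 SD | 42-70% | 66-92% |

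**Counterbalanced, plain paired test.** Half the subjects have shift +d and half −d, so the mean shift is 0. The variance of change rises from 2(1 − r) to about 2(1 − r) + d². That is 0.04 / 0.8 = 5% at d = 0.2, r = 0.6, and 0.25 / 0.4 = 62.5% at d = 0.5, r = 0.8. The test becomes conservative: 2-4% at r = 0.7 for d = 0.2 to 0.5.

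**Counterbalanced, with form order as a factor.** The extra variance is removed, at the price of one degree of freedom. The rejection rate is about 5% throughout.

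**Fixed order, between-arm test of change, 20 v 20.** The form effect is the same in both arms and cancels. At r = 0.7 the simulated rates are 5.2%, 4.8% and 5.1% for d = 0.2, 0.3 and 0.5.

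**The case against.** The strongest reply is that the text does not fix the order. Under counterbalancing, each subject also gets the other version at follow-up, so the sentence fits both designs. This stands in part. A reader might infer that every subject certainly has a standard form first and the alternate second; the document never says so. Fixed order is the natural reading of wording that ties the alternates to follow-up, combined with silence on counterbalancing, but it remains an inference.

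Second, the tests are redacted and are described as standard measures, so the forms may be well equated. This also stands. Nothing in the document shows that they differ, and at 0.1 SD the inflation is small.

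Third, Bonferroni correction is allowed when needed. With ten tests (an assumption), alpha is 0.005, and a 0.2 SD form difference gives 1.6-2.9% (n = 12) or 2.8-6.3% (n = 20). Those rates are lower, but they are still at least three times the 0.5% nominal level, and the bias in the mean change is untouched.

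Fourth, the placebo arm meets the same forms. A reader might therefore infer that the randomised comparison itself is biased. It would not be: a between-arm contrast of change cancels the form effect. The reply fails as a defence of the plan only because no such contrast is specified.

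Fifth, counterbalancing does not rescue an uncontrolled phase, where practice, time and expectancy stay mixed with any product effect. That is correct, and limits what the fix can claim.

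Finally, the mention of two follow-up visits looks like leftover wording, because every other description of the schedule gives baseline and week 6 only. It does not support an inference that a third session is planned.

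**Conclusion.** The concern holds for the tests that have two forms. As the text naturally reads, form and time coincide, and the only planned test carries any form difference straight into the Aim 2 estimate. This affects the open-label phase and within-arm results of the double-blind phase. It does not extend to the whole battery, nor to a comparison of the two arms.

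The consequence ranges from slight to severe (table above) and depends wholly on an unknown form difference. It should be read as a conditional risk, not as a demonstrated bias. Since the remedy is cheap and the effect cannot be separated afterwards within one arm, the plan should be changed. The inconsistent count of follow-up visits is minor, but it bears on how many forms are needed.

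**What to change.** 1. **Neuropsychological Assessment.** For each test with two forms, assign order A-B or B-A half and half: 6/6 if 12 enter the open-label phase, and 10/10 within each double-blind arm. Record the form given at each session. Prepare the double-blind order list together with the treatment list, without revealing allocation. The Double-Blind Trial section describes treatment assignment as alternating, so simply alternating the forms as well could tie form order to arm. If order is already counterbalanced, say so.
2. **Statistical Approaches.** Analyse change with form order as a factor. Without it, the variance of change rises as shown above.
3. **Double-blind phase.** Prespecify a between-arm comparison of week-6 scores, adjusted for baseline score and form order. This protects the randomised result even if form order stays fixed.
4. **Open-label phase.** State that counterbalancing removes only the form effect, and that practice and time effects remain.
5. Reconcile the reference to two follow-up visits with the two time points in the same section.

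The cost is an order list, one recorded variable, one degree of freedom and a short revision of two sections. No extra testing or subjects are needed. For anyone already tested, order cannot be changed, and only the forms used can be recorded and reported.

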#### Buccal Swab

Buccal swab samples will be collected at the baseline visit using Endo-DNA kits and used for genotyping.

For studies involving treatment or diagnosis, provide information about standard of care at Partners (e.g., BWH, MGH) and indicate how the study procedures differ from standard care. Provide information on available alternative treatments, procedures, or methods of diagnosis.

Standard of care for anxiety treatment includes medications, such as antidepressants, buspirone, and benzodiazepines, as well as psychotherapy. This study is an investigation of a plant-derived compound that has promise in the treatment of anxiety. Subjects will not be asked to change their current treatment regimen to participate in this study (i.e. discontinue other medications); this study will add CBD to their current regimen.

Describe how risks to subjects are minimized, for example, by using procedures which are consistent with sound research design and which do not unnecessarily expose subjects to risk or by using procedures already being performed on the subject for diagnostic or treatment purposes.

Risks to subjects will be minimal throughout this study; please see below for detailed explanation of foreseeable risks and discomforts. The components of this study, including the clinical rating scales, neurocognitive tasks, and MR scanning have previously been used by the investigator in multiple studies. The administration of CBD will be low risk due to the add-on design of the study; patients will proceed with their treatment as usual, with CBD or placebo added to their medication regimen. See below for a detailed explanation of the risks of CBD administration in this population.

Describe explicitly the methods for ensuring the safety of subjects. Provide objective criteria for removing a subject from the study, for example, objective criteria for worsening disease/lack of improvement and/or unacceptable adverse events. The inclusion of objective drop criteria is especially important in studies designed with placebo control groups.

The side-effect profile of CBD is extremely low, and adverse events are not anticipated. The daily dose is the same as another protocol using a cannabis-derived sublingual solution (████████), and no serious adverse events have been reported in that study. Subjects may withdraw from the study at any time and for any reason. A subject's participation in the trial will end if they report adverse effects of CBD or placebo administration and wish to leave the study, or if study staff determine that study termination is appropriate due to adverse events. Additional termination criteria include: subject does not use solution as directed; subject sustains a significant head injury; any study exclusions are met (i.e. change in medical status, pregnancy, etc.)

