### **Double-Blind Trial**

Individuals will be assessed in-person at baseline and weekly for 6 weeks of treatment with compounds administered as sublingual solutions in a double-blind, randomized procedure: subjects will receive either the CW solution or matched placebo. At the weekly visits throughout the treatment period, individuals will complete clinical scales and have a check-in with study staff.

In addition to clinical ratings and a check-in with study staff, neuropsychological testing will be performed at baseline and week 6 in order to assess cognitive performance. Finally, a subset of individuals will receive an hour-long MRI scan at baseline and week 6, with both resting state and task-related functional magnetic resonance imaging (fMRI) in each MRI session. In addition, a brief diffusion tensor imaging (DTI) sequence will also be acquired to examine white matter fiber tract integrity, and magnetic resonance spectroscopy (MRS) will be conducted to examine levels of certain metabolites in the brain. Subjects will also provide a buccal swab sample for genetic analysis at the baseline visit.

[figure not shown]
At the end of the baseline visit, eligible subjects will be randomized to either CW solution or placebo using a standard alternating procedure in accordance with the McLean Pharmacy. Subjects will be instructed on how to administer the compound, as described above.

For both the open-label and double-blind trials, the baseline and the final study visits are estimated to take approximately 3-4 hours, with the weekly visits in the interim estimated to take approximately 1 hour, and 15 minutes for phone check-ins, for a total of approximately 10-12 hours required to complete all possible visits. Urine samples will be collected at every other visit (Visits 1, 3, 5, and 7) to measure THC via GCMS (Quest Diagnostics) and to monitor for the presence of other substances throughout the study. Female subjects will be informed that their sample will also be used to confirm negative pregnancy (HCG) status; if at any point their urine tests positive for HCG, they will be excluded from the study. We are currently in communication with several groups that may be able to assess for CBD in urine; we hope to utilize one of these groups to quantify CBD in urine throughout the study.

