#### Clinical Ratings

The Structured Clinical Interview for DSM-V Patient Version (SCID-P) and the SCID-P Substance Abuse/Dependence Module or the Quick Structured Clinical Interview for DSM-V Disorders (QuickSCID) will be administered to all study participants during visit 1 by the Principal Investigator, a Clinical Neuropsychologist or trained Clinical Research Assistant. Subjects will also complete clinical rating scales and questionnaires that have been shown to provide reliable estimates of current clinical state and are easily administered. They will also complete quality of life measures. All subjects will be given the following measures at the baseline and final visits that take approximately one hour to complete:

Subjects will also complete a subset of these measures, specifically the anxiety and mood-related measures [REDACTED], along with the SEQ, at each weekly visit. An Abuse Liability Rating Scale (ALR) will be completed at V3 and V7.

Please note that if suicidality is endorsed spontaneously, on any of the clinical scales, or during the SCID or weekly check-ins with study staff, the patient will be immediately assessed for suicidality risk. Please see “Suicidality SOP” attachment for further information.

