## DATA AND SAFETY MONITORING

Describe the plan for monitoring the data to ensure the safety of subjects. The plan should include a brief description of (1) the safety and/or efficacy data that will be reviewed; (2) the planned frequency of review; and (3) who will be responsible for this review and for determining whether the research should be altered or stopped. Include a brief description of any stopping rules for the study, when appropriate. Depending upon the risk, size and complexity of the study, the investigator, an expert group, an independent Data and Safety Monitoring Board (DSMB) or others might be assigned primary responsibility for this monitoring activity.

NOTE: Regardless of data and safety monitoring plans by the sponsor or others, the principal investigator is ultimately responsible for protecting the rights, safety, and welfare of subjects under his/her care.

Data analyses will be conducted on the open-label phase of the study prior to initiating the double-blind phase in order to ensure that patients derive clinical benefit from the dose selected. Specifically, in conjunction with [REDACTED], we will assess clinical response after the first 5 patients have completed their 6 week trial. If we do not see clinical improvement based on a review of clinical scales, subjective reports and performance, we will consider increasing the dose to 1 droppers two times a day for a total of 60 mg CBD per day. Clinical improvement will be defined as a 15% reduction in BAI scores from baseline. Findings will be used to inform the double blind phase of the study, which would not begin until adequate dose/response is achieved. An amendment would be submitted to the IRB for approval prior to adjusting the dose of CBD.

In the unlikely event that an adverse event occurs, it will be reported to the primary investigator and the Institutional Review Board's guidelines will be followed to ensure adequate reporting and response. All adverse events will be reported to the Partners Healthcare Internal Review Board for their records. There are currently no plans to utilize a Data Safety Monitoring Board (DSMB) due to the extremely low side-effect profile of CBD, but if the IRB deems that an independent DSMB is necessary, the investigators would be happy to suggest individuals who are appropriate or to consider outside suggestions from IRB members.

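### Non-adherence is a termination criterion, no later outcome assessment is provided for, and no analysis population or missing-data rule is named, so week-6 comparisons would most likely omit the subjects removed

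*Combined protocol and SAP*

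**What the plan says.** The safety and removal criteria close the Research Design and Methods text (they are printed under the Buccal Swab heading). After describing when participation ends because of adverse events, they add: "Additional termination criteria include: subject does not use solution as directed". No threshold for directed use is given. Adherence is recorded in self-completed daily diaries. For subjects who leave early, Recruitment Procedures describes payment for the part completed. No section schedules an assessment after termination.

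Statistical Approaches says that clinical and neuropsychological data "will be assessed using 2-tailed paired *t*-tests to compare follow-up timepoints to baseline values", with a signed-rank test as the non-parametric alternative. It names no analysis population, no handling of missing values and no as-randomised principle. Nothing in that section is marked as redacted.

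The outcomes are timed as follows:
- **Anxiety and mood:** rated weekly. Clinical Ratings says "Subjects will also complete a subset of these measures, specifically the anxiety and mood-related measures" are completed at each weekly visit.
- **Quality of life:** baseline and final visit. "After 6 weeks of treatment, participants will complete final clinical scales and quality of life measures".
- **Cognition:** "Individuals will complete neuropsychological assessments at two time points; at baseline and after 6 weeks of treatment". The same section also refers to both follow-up visits, so the schedule is not fully clear.
- **MRI:** "a subset of individuals will receive an hour-long MRI scan at baseline and week 6".

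**The concern.** Adherence is behaviour after randomisation and may be related to how the subject is doing. A rule that ends participation on that behaviour, combined with a test that needs a week-6 value, makes the week-6 sample depend on post-randomisation events.

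If subjects who feel no benefit are the ones who stop using the solution, those left at week 6 look better than the group that started. Each arm's improvement is then overstated, and unequal removal would also bias the CBD-placebo difference. If better responders are removed, the bias runs the other way. If removal is unrelated to response, only precision is lost. With 20 subjects per arm, each missing week-6 outcome is 5% of an arm.

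Quality of life and MRI are the most exposed, because no measurement is scheduled between baseline and the final visit. A subject removed earlier contributes no change score for them.

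**Working it through.** The plan states no removal rate, SD, power or adherence-outcome link, so there is no figure to reproduce. What follows is an illustration.

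**Input from the protocol:** 20 per arm (Research Design and Methods).

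**Assumptions:** no true mean change; changes from baseline are normal with SD 1 and correlation ρ between any two weeks; k of 20 subjects are removed at random from the 10 less improved at week 2; the rest are analysed at week 6.

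**Step 1, bias within an arm.** The expected mean of the lower half of 20 standard normal values is -0.767. All 20 have expected mean 0, so those kept have expected week-2 mean k × 0.767 / (20 - k):
- k = 2: 2 × 0.767 / 18 = 0.085
- k = 4: 4 × 0.767 / 16 = 0.192
- k = 6: 6 × 0.767 / 14 = 0.329

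Multiplying by ρ gives the false improvement at week 6. Type I error of the paired t-test (nominal 5%, two-sided) is from 40,000 simulated trials per case:

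| Removed | ρ = 0.3 | ρ = 0.5 | ρ = 0.7 |
|---|---|---|---|
| 2 of 20 (10%) | 0.026 SD, 5.0% | 0.043 SD, 5.3% | 0.060 SD, 5.4% |
| 4 of 20 (20%) | 0.058 SD, 5.4% | 0.096 SD, 6.3% | 0.134 SD, 7.4% |
| 6 of 20 (30%) | 0.099 SD, 6.5% | 0.164 SD, 8.6% | 0.230 SD, 12.3% |

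Simulated biases agree with the formula to within 0.003 SD. Removing the more improved half gives the same size with opposite sign. Random removal gives no bias.

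**Step 2, bias between arms.** Statistical Approaches states no between-arm test, so a two-sample t-test is assumed. The bias is the difference between the two arms' entries, for ρ = 0.5 and 0.7:
- 20% against 10% removed: 0.096 - 0.043 = 0.053 and 0.134 - 0.060 = 0.074 SD (type I error 5.0% to 5.3%)
- 30% against 10% removed: 0.164 - 0.043 = 0.121 and 0.230 - 0.060 = 0.170 SD (6.2% to 7.0%). With an assumed SD of 8 BAI points, 0.121 × 8 = 1.0 to 0.170 × 8 = 1.4 points.
- Equal removal: no bias.

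**Step 3, precision.** For the same assumed test, the difference detectable with 80% power is 0.91 SD with 20 per arm, 0.96 with 18, 1.02 with 16 and 1.10 with 14.

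**Step 4, what the weekly scores can repair.** A likelihood estimate was formed by regressing week 6 on weeks 1 and 2 in those kept and applying the fit to everyone. When removal depends on the observed week-2 score, its bias is at most 0.003 SD. When removal depends on an unobserved week-3 score, about 0.01 to 0.06 SD remains (10% to 30% removed, ρ 0.3 to 0.7).

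**The case against.** The strongest reply is that this is silence, not a stated completer analysis. The protocol never says that assessment stops after termination for non-adherence, or that removed subjects are left out. That stands, and the point is worded accordingly. The inference is still the natural one: the criterion follows a sentence about participation in the trial ending, and a paired week-6 test cannot use a subject without a week-6 value.

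The effect may also be small. At 10% removal the paired test stays near 5%, and the between-arm bias is minor unless removal is both frequent and unequal. Use other than as directed also includes over-use, which need not follow poor response. All of this stands.

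The paired-test error rates assume zero mean change. Subjects enrolled on elevated scores may improve through placebo response or regression to the mean whatever the removals, so those percentages do not describe this trial's actual error. The biases in SD units come on top of such improvement.

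Three stronger readings are tempting and not supported:
- A reader might infer from Data and Safety Monitoring, which says "we will assess clinical response after the first 5 patients have completed their 6 week trial", that completers are the analysis population. That sentence only times an open-label dose check.
- A reader might infer that any reported adverse effect leads to removal. The rule also requires that the subject wishes to leave or that staff judge termination appropriate.
- A reader might infer that all data from removed subjects are lost. Weekly ratings made before removal exist and remain usable, although no rule brings them into a week-6 analysis.

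**Conclusion.** The concern holds in limited form. Followed as written, the plan would most likely base week-6 comparisons on subjects not removed for non-adherence. If removal follows poor response, within-arm improvement is overstated by about 0.04 to 0.06 SD at 10% removal (type I error about 5%), 0.10 to 0.13 SD at 20% (6% to 7.5%) and 0.16 to 0.23 SD at 30% (about 9% to 12%), for correlations of 0.5 to 0.7.

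These figures rest on assumed removal rates, an assumed link to week-2 response and no true change. The documents support neither a rate nor a direction, so they do not show that the trial's result is biased. The change is worth making because it is cheap. Confidence is medium.

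**What to change.** **Removal criteria.** Leave every clinical and product-stopping criterion unchanged. Add that subjects terminated for non-adherence who do not withdraw consent are asked to complete the weekly ratings already scheduled and, where feasible, the week-6 quality-of-life, cognitive and MRI assessments.

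**Statistical Approaches.** Analyse all randomised participants in their assigned arm using all available weekly BAI scores, for example with a mixed model containing arm, week, arm-by-week and baseline BAI. Keep an adherent-only analysis as secondary. Report removals by arm, week and reason.

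Both parts are needed. The model removes the bias only if removal depends on observed scores, and it cannot help quality of life or MRI, which have no scheduled interim measure.

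**Cost.** Besides the wording, payments under Recruitment Procedures are at most 5 × $30 + $75 + $50 = $275 per retained participant (the $50 completion bonus only if applicable), or $275 + $75 = $350 with the final MRI. For removal after the week-2 visit they are 3 × $30 + $75 + $50 = $215, or $290 with MRI. If eight people were retained, the maximum is 8 × $275 = $2,200 to 8 × $350 = $2,800. Staff time is at most 8 to 9 hours each (five visits of about 1 hour plus a final visit of 3 to 4 hours). MRI participants need about an hour of scanner time, and the protocol does not say whether that falls within the final visit. All these visits are already planned for a completer. The downside is an estimate that may be diluted compared with adherent-only results.
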